7.6 DATA REPORTING

All study data will be recorded onto case report forms (electronic or paper) designed for the study. CRFs can be signed by the investigator either by paper signature or by electronic signature. The CRF may be the source document for some data and each site will document this with a note to file describing in which cases source data will be recorded directly onto the CRF. If paper CRFs are used, all CRFs will be completed in a legible manner in black/blue ink.

Any corrections to the CRFs will be made by drawing a single line through the incorrect entry, recording the correct information, and initialing and dating the change. The CRFs and/or data entered in the EDC system will be reviewed by the Study Monitor.

All clinical data generated in the study will be submitted to RxSight or designated CRO for quality assurance review and statistical analysis. All CRFs and/or data entered into the EDC system will be reviewed for completeness and evident recording errors will be rectified by contact with the appropriate clinical site. Computerized data checks will be used to identify unusual data entries for verification prior to statistical analysis.

To minimize the amount of missing data, investigators will be trained on the deleterious effect that missing data have on trial integrity and credibility and that missing data could diminish the scientific value of all subjects' altruistic contributions.

7.7 STUDY COMPLETION PROCEDURES

A study Exit Form must be completed for all subjects enrolled in the study upon subject completion, withdrawal or discontinuation.

7.7.1 SUBJECT COMPLETION

Subjects are considered to have completed the study if they have completed the Postop Month 3 or later visit.

Subjects with ocular serious adverse events or adverse device effects that are unresolved at study exit should continue to be followed until resolution of the event or until they are stable per the investigator's evaluation.

7.7.2 SUBJECT WITHDRAWAL PRIOR TO IMPLANTATION

Subjects may be withdrawn from the study prior to implantation if they do not meet all inclusion/exclusion criteria (screen failures) or decide not to participate in the study.

7.7.3 SUBJECT WITHDRAWAL DUE TO INTRAOPERATIVE COMPLICATIONS PRIOR TO IMPLANTATION

Subjects that meet all inclusion/exclusion criteria but do not undergo implantation of the LAL due to intraoperative complications prior to introduction of the LAL will be followed to resolution of any adverse events and then exited from the study.

7.7.4 SUBJECT DISCONTINUATION AFTER IMPLANTATION

After implantation, subjects may not be withdrawn from the study unless the study lens has been explanted. In the case of an explant, the investigator should continue follow-up for a period that ensures no adverse consequences have resulted. When possible, all necessary clinical assessments will be performed prior to the Subject exiting the study even if the assessment was not scheduled at that particular visit.

Subjects may be discontinued from the study only when the study lens has been explanted or subject has deceased. The reason for discontinuation will be recorded on the appropriate study worksheet. Subjects who are discontinued from the study will still be a part of the study analyses up until the point they are exited.

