8 STATISTICAL METHODS

8.1 POPULATIONS FOR ANALYSIS

Exploratory effectiveness analyses will be performed on all eyes as specified.

Safety analyses will be performed on observed data for all eyes of subjects who sign the informed consent and the procedure was attempted which is defined as the point at which the LAL makes contact with the eye. No imputation will be performed.

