8.1.1 EXPLORATORY EFFECTIVENESS PARAMETERS

UCDVA

Monocular and binocular UCDVA will be presented with the number and percent of eyes that fall into each category of visual acuity performance (e.g. 20/20 or better, 20/25 or better, 20/32 or better, etc.) at each visit tested. Number and percent of eyes for subjects that only received spherical/sphero-cylindrical adjustments and for subjects that received a presbyopia adjustment will be presented separately.

UCIVA, UCNVA, DCIVA, and DCNVA

Monocular and/or binocular UCIVA, UCNVA, DCIVA, and DCNVA for subjects that received a presbyopia adjustment will be presented with the number and percent of eyes that fall into each category of visual acuity performance (e.g. 20/20 or better, 20/25 or better, 20/32 or better, etc.) at each visit tested.

Pseudo Accommodation

The mean acuity across all subjects that received a presbyopia adjustment will be calculated and plotted separately. The mean, standard deviation, and confidence intervals for each point on the curve will be reported.

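### Eyes explanted after adjustment drop out of the late acuity percentages, and monocular UCDVA through a replacement lens is not excluded; success may be slightly overstated

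*Combined protocol and SAP*

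**What the plan says.** Section 5 sets two headline proportions, each at Month 1-2 and at Month 3 or later. For subjects with only spherical/sphero-cylindrical adjustments, it is the percentage of eyes with UCDVA of 20/20 or better. For bilaterally implanted subjects with a presbyopia adjustment, it is the proportion of subjects who meet binocular distance, intermediate and near thresholds together.

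Section 7.7.4 governs who can leave after implantation: "Subjects may be discontinued from the study only when the study lens has been explanted or subject has deceased". On their data it says: "Subjects who are discontinued from the study will still be a part of the study analyses up until the point they are exited". It also asks for continued observation ("In the case of an explant, the investigator should continue follow-up for a period that ensures no adverse consequences have resulted") and for a last set of measurements ("When possible, all necessary clinical assessments will be performed prior to the Subject exiting the study even if the assessment was not scheduled").

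Section 8.1 says of effectiveness: "Exploratory effectiveness analyses will be performed on all eyes as specified". Safety has a precise set, tied to whether the "procedure was attempted which is defined as the point at which the LAL makes contact with the eye". The sentence "No imputation will be performed" closes that safety paragraph. Section 8.1.1 gives number and percent of eyes per acuity category, its wording ending "20/32 or better, etc.) at each visit tested". None of these sections says how an explanted eye is to be counted.

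**The concern.** An eye that has been explanted and exited is not tested at a later visit, so it is in neither the numerator nor the denominator there. Section 10.6 names one reason for removal that is tied to the outcome itself: adjustment or lock-in may worsen vision enough that the lens has to be taken out and replaced. If such eyes are left out, the remaining eyes are a selected group and the late percentages lean upward.

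There is a second route for the monocular measure. Discontinuation after explant is permitted, not required, and follow-up is to continue for a period that is not fixed. An eye with a replacement lens could therefore attend a visit and have its UCDVA recorded. No rule keeps that reading out of the 20/20 count, where it would credit the LAL and LDD with another lens's result.

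These descriptive percentages are the study's main effectiveness output, and Section 12.9 allows for their publication.

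**Working it through.** The plan has no figure to reproduce. Section 9.1 states that there is no hypothesis-driven endpoint or associated sample size, and the documents give no explant rate, success rate or group split. What follows is an illustration on assumed inputs.

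**Inputs**
- Maximum of 200 eyes (Section 6).
- Assumed split that fits the maximum: 100 eyes with spherical/sphero-cylindrical adjustment only, and 50 bilateral presbyopia subjects; 100 + 2 × 50 = 200.
- Assumed success among those tested, p = 80%, varied from 60% to 90%.
- Assumed number explanted after adjustment, k = 1, 2 or 5 (eyes for UCDVA; subjects with an explanted eye for the composite). No other data are missing.

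**Route 1: explants leave the denominator.** Successes are p(N − k). Observed-only percentage: p(N − k)/(N − k) = p. With explants as non-success: p(N − k)/N. The difference is p × k/N.

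| Outcome | N | k | Observed only | Explants as non-success | Difference |
|---|---|---|---|---|---|
| UCDVA 20/20 | 100 eyes | 1 | 80% | 79.2% | 0.8 points |
| UCDVA 20/20 | 100 eyes | 2 | 80% | 78.4% | 1.6 points |
| UCDVA 20/20 | 100 eyes | 5 | 80% | 76.0% | 4.0 points |
| Composite | 50 subjects | 1 | 80% | 78.4% | 1.6 points |
| Composite | 50 subjects | 2 | 80% | 76.8% | 3.2 points |
| Composite | 50 subjects | 5 | 80% | 72.0% | 8.0 points |

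The last row needs 5/50 = 10% of subjects to have an explant, so it is an outer case. With k = 2 and p from 60% to 90%, the difference runs from 0.6 × 2/100 = 1.2 to 0.9 × 2/100 = 1.8 points (N = 100), and from 2.4 to 3.6 points (N = 50). If all 200 eyes were in the UCDVA group, 5 explants at 80% would give 0.8 × 5/200 = 2.0 points.

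Whole counts agree: 78/98 = 79.6% against 78/100 = 78.0%, and 38/48 = 79.2% against 38/50 = 76.0%.

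**Route 2: replacement-lens acuity is scored (monocular UCDVA).** In the worst case every explanted eye reads 20/20 or better, and the excess over non-success is k/N. With 78 successes and 2 explants in 100 eyes: (78 + 2)/100 = 80.0% against 78.0%, or 2.0 points.

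**Scale.** The 95% half-width at 80% is 1.96 × √(0.8 × 0.2/n): about 7.8 points for n = 100 and 11.1 points for n = 50. With two explants, the shift is well inside sampling error.

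**The case against.** The strongest reply is that the plan does contain a rule. Section 5 defines both groups, Section 8.1.1 repeats the split for UCDVA and counts eyes at visits tested, and Section 7.7.4 keeps people in until exit. That is an observed-case analysis, and for an exploratory study of outcomes after adjustment it is a legitimate descriptive choice. Explants stay visible in the safety set and in expedited reporting (Section 10.4.3), reasons for discontinuation are recorded, and tested n can be recovered from number and percent. All of this stands, and it limits the stakes. It does not remove the upward lean, and no explant count is planned beside the percentages.

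On replacement lenses, Table 1 footnote 1 restricts the binocular tests to subjects with both eyes in the study and successfully implanted. Its application to a later explant is arguable, but it makes replacement-lens scoring of the composite less likely. Loss from the denominator is the main route there. The monocular UCDVA row carries no such footnote.

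The pre-exit measurements soften the loss. They are made only when possible, however, and no rule assigns them to a visit. Month 1-2 is timed from final lock-in, so it has no date for an eye explanted before lock-in.

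Section 10.6 also mentions explant because a pupil cannot be dilated. Dilation is needed for adjustment as well as lock-in, so that explant may come before any adjustment and fall outside both Section 5 groups. The argument does not rely on it.

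**Conclusion.** The point holds and is minor. As written, an eye explanted after adjustment and exited leaves the late percentages, and monocular acuity through a replacement lens is not excluded. Since one foreseen reason for explant is worsened vision, the lean is toward overstated success. The size is p × k/N: 1.6 points for 2 of 100 eyes and 3.2 points for 2 of 50 subjects at 80% success. The rate, success and split are all assumed. If explants are few, the effect is small. No test or error rate is touched.

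A reader might infer more than the documents support:
- *That the effectiveness denominator is undefined.* The Section 5 groups and the wording of Section 8.1.1 imply one; only the treatment of explants is missing.
- *That every explant is a treatment failure.* Section 10.6 also describes a scratched or misplaced lens removed before light treatment.
- *That the fellow eye of an explanted eye is lost as well.* Discontinuation is optional, Section 7.4 schedules follow-up for each study eye, and Section 9.2 counts eyes; these favour its continued follow-up.
- *That explants are known to be common.* Section 2.1 reports a raised rate of secondary surgical interventions in the earlier trial but does not say how many were explants.

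**What to change.** Add an analysis rule to Sections 7.7.4 and 8.1.1, applied separately to each Section 5 group:

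1. Count an eye explanted after at least one adjustment (for the composite, a subject with such an eye) as not meeting the criterion at later visits, and give the observed-only percentage beside it.
2. List acuity measured after explant or lens replacement, but never count it as success.
3. Show the number explanted beside each percentage, and list eyes explanted before any adjustment separately with the reason.

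The cost is wording in two sections, a little programming and one extra table column. No visit, test or clinical procedure changes. The downside is that the success percentages become slightly less favourable and two are shown where one was planned.

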7.7.5 LOST TO FOLLOW-UP

Subjects for which the final post-operative case report form is overdue and who refuse to be followed, or have difficulty being followed, or cannot be contacted despite extensive written and telephone follow-ups to determine the final clinical outcome, will be considered lost to follow-up. Sites must make a minimum of three documented attempts via telephone, email, or regular mail to contact the subject. If the subject does not reply to any of these attempts, the site must send a letter by certified mail (with a request for notification of receipt of delivery) to the subject. If a subject is non-responsive to these follow-up attempts, the subject will be considered to be lost to follow-up.

7.7.6 STUDY TERMINATION

The study may be stopped at any time by the Sponsor(s) for reasonable cause with appropriate notification. Conditions that may warrant study termination include, but are not limited to the following:

- Safety concerns. Clinical data from the study will be monitored to assure the safety of enrolled subjects.

If the clinical study is prematurely terminated, the Sponsor will inform the Investigator, Ethics Committee, and other appropriate regulatory bodies. If the Sponsor terminates the study for safety reasons, it will immediately notify the Investigator, Ethics Committee, and other appropriate regulatory bodies and provide an explanation of the reasons for termination. The Investigator will be provided with instructions for study termination and applicable subject follow-up. The Sponsor will continue to provide resources to fulfill the Clinical Study Plan obligations for follow-up of the subjects enrolled in the study.

8 STATISTICAL METHODS

8.1 POPULATIONS FOR ANALYSIS

Exploratory effectiveness analyses will be performed on all eyes as specified.

Safety analyses will be performed on observed data for all eyes of subjects who sign the informed consent and the procedure was attempted which is defined as the point at which the LAL makes contact with the eye. No imputation will be performed.

8.1.1 EXPLORATORY EFFECTIVENESS PARAMETERS

UCDVA

Monocular and binocular UCDVA will be presented with the number and percent of eyes that fall into each category of visual acuity performance (e.g. 20/20 or better, 20/25 or better, 20/32 or better, etc.) at each visit tested. Number and percent of eyes for subjects that only received spherical/sphero-cylindrical adjustments and for subjects that received a presbyopia adjustment will be presented separately.

UCIVA, UCNVA, DCIVA, and DCNVA

Monocular and/or binocular UCIVA, UCNVA, DCIVA, and DCNVA for subjects that received a presbyopia adjustment will be presented with the number and percent of eyes that fall into each category of visual acuity performance (e.g. 20/20 or better, 20/25 or better, 20/32 or better, etc.) at each visit tested.

Pseudo Accommodation

The mean acuity across all subjects that received a presbyopia adjustment will be calculated and plotted separately. The mean, standard deviation, and confidence intervals for each point on the curve will be reported.

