5 OUTCOME PARAMETERS

The following visual performance parameters will be collected and summarized for subjects that received only spherical/sphero-cylindrical adjustments.

- % of eyes with UCDVA of 20/20 or better at Postop Month 1-2 and the Postop Month 3 or later visit.

The following visual performance parameters will be collected and summarized for subjects that were bilaterally implanted with the LAL and received a presbyopia adjustment.

- Proportion of subjects simultaneously with (1) Binocular UCDVA of 20/20 or better and (2) Binocular UCIVA of 20/25 or better and (3) Binocular UCNVA of 20/40 or better at Postop Month 1-2 and the Postop Month 3 or later visit.
- Change in pseudoaccommodation (D) at Postop Month 1-2 and the Postop Month 3 or later visit from pre-light adjustment at Postop Week 3

Additional analyses may be performed. Clinical data for subjects receiving only spherical/sphero-cylindrical adjustments and subjects receiving a presbyopia adjustment will be summarized and analyzed separately.

SAFETY PARAMETERS

- Incidence of cumulative ocular serious adverse events defined per ISO 11979-7.

The incidence of all other adverse events will also be presented.

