Vision Quality Measurement (HD Analyzer)				X			X		X	X	
Undilated Distance Viewing Pupil Diameter	X			X					X	X	
Binocular UCDVA				X ¹					X ¹	X ¹	
Monocular uncorrected distance visual acuity (UCDVA)	X		X	X	X	X	X	X	X	X	X
Manifest Refraction	X			X	X	X	X	X	X	X	
Monocular best corrected distance visual acuity (BCDVA)	X			X	X	X	X	X	X	X	
Ocular Dominance Test	X			X							
Pseudo Accommodation Testing				X			X ²		X ²	X ²	
Mesopic binocular distance corrected contrast sensitivity testing				X					X ⁴	X ⁴	
Mesopic monocular distance corrected contrast sensitivity testing				X					X ⁴	X ⁴	
Photopic binocular distance corrected contrast sensitivity testing				X					X ⁴	X ⁴	
Photopic monocular distance corrected contrast sensitivity testing				X					X ⁴	X ⁴	
Monocular distance corrected 10% low contrast intermediate visual acuity (photopic)				X					X ²	X ²	
Monocular distance corrected intermediate visual acuity (DCIVA)				X	X ^{2,4}	X ^{2,4}	X ²		X ²	X ²	
Monocular distance corrected intermediate visual acuity (DCIVA) with +1.50 D add				X	X ^{2,4}	X ^{2,4}	X ²		X ²	X ²	

Visits	Preop	Operative	Postop Day 1	Postop Week 3	Adjustment #2 (if needed)	Adjustment #3 (if needed)	Lock-in #1	Lock-in #2 (if needed)	Postop Month 1-2	Postop Month 3 or later Visit	Unscheduled Visit ¹
Monocular uncorrected intermediate visual acuity (UCIVA)				X	X ^{2,4}	X ^{2,4}	X ²		X ²	X ²	
Binocular UCIVA				X ¹	X ^{1,2,4}	X ^{1,2,4}	X ^{1,2}		X ^{1,2}	X ^{1,2}	
Undilated Intermediate Viewing Pupil Diameter				X	X ^{2,4}	X ^{2,4}			X ²	X ²	
Monocular distance corrected 10% low contrast near visual acuity (photopic)				X					X ²	X ²	
Monocular distance corrected near visual acuity (DCNVA)				X	X ^{2,4}	X ^{2,4}	X ²		X ²	X ²	
Monocular distance corrected near visual acuity (DCNVA) with +2.50 D add				X	X ^{2,4}	X ^{2,4}	X ²		X ²	X ²	
Monocular uncorrected near visual acuity (UCNVA)				X	X ^{2,4}	X ^{2,4}	X ²		X ²	X ²	
Binocular UCNVA				X ¹	X ^{1,2,4}	X ^{1,2,4}	X ^{1,2}		X ^{1,2}	X ^{1,2}	
Undilated Near Viewing Pupil Diameter				X	X ^{2,4}	X ^{2,4}	X ²		X ²	X ²	

Intraocular Pressure	X		X	X	X	X	X	X	X	X	X
Slit Lamp Exam	X		X	X	X	X	X	X	X	X	X
Fundus Exam	X			X							
Aberrometry				X	X	X	X		X	X	
Dilated Pupil Diameter	X			X	X	X	X	X			
Adverse Events		X	X	X	X	X	X	X	X	X	X

¹ Only performed on subjects with both eyes enrolled and successfully implanted.

² Only performed on subjects receiving a presbyopia treatment.

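### Monocular acuity is counted per eye but grouped by the subject's adjustments, so if a subject has a presbyopia adjustment in one eye only, the sphere-only fellow eye enters the presbyopia tables

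*Combined protocol and SAP*

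**What the plan says.** Below, *sphere-only* means an eye or subject given only spherical or sphero-cylindrical adjustments.

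- **Unit of count.** Section 8.1.1 on UCDVA: "Monocular and binocular UCDVA will be presented with the number and percent of eyes that fall into each category of visual acuity performance".
- **Grouping for UCDVA.** Same section: "Number and percent of eyes for subjects that only received spherical/sphero-cylindrical adjustments and for subjects that received a presbyopia adjustment will be presented separately".
- **Grouping for the other acuities.** Section 8.1.1 states that monocular and/or binocular UCIVA, UCNVA, DCIVA and DCNVA "for subjects that received a presbyopia adjustment will be presented with the number and percent of eyes" in each acuity category.
- **Listed outcomes.** Section 5 introduces the sphere-only outcome with "The following visual performance parameters will be collected and summarized for subjects that received only spherical/sphero-cylindrical adjustments", and the outcome is the percentage "of eyes with UCDVA of 20/20 or better at Postop Month 1-2 and the Postop Month 3 or later visit". The presbyopia outcomes are for "subjects that were bilaterally implanted with the LAL and received a presbyopia adjustment". They are a per-subject composite of binocular acuities and a change in pseudoaccommodation.
- **General split.** Section 5 adds that clinical data for "subjects receiving only spherical/sphero-cylindrical adjustments and subjects receiving a presbyopia adjustment will be summarized and analyzed separately".
- **Who is tested.** Footnote 2 to Table 1 (Section 7.5) attaches to the post-adjustment monocular intermediate and near tests: "Only performed on subjects receiving a presbyopia treatment".

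**The concern.** The counting unit and the grouping variable sit at different levels. For a binocular measure the subject is the natural unit and grouping by subject is right. For a monocular measure the natural question is how an eye with a given adjustment sees, and the subject's history does not answer it when the two eyes were treated differently.

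Monocular DCIVA and DCNVA are the measures closest to the effect of a presbyopia adjustment in the eye that received it. If a row labelled presbyopia also holds eyes without that adjustment, its percentage is a blend of two kinds of eye in unknown proportion. The study has no hypothesis test and no primary effectiveness endpoint, so these descriptive percentages are themselves part of the result.

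**Working it through.** The plan has no figure to reproduce: Section 9.1 says there are no hypothesis-driven endpoints and no associated sample size. The check is a reading of the grouping rule, followed by an illustration.

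**Step 1: apply the rule to each kind of subject.**

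| Subject | Sphere-only group? | Presbyopia group? |
|---|---|---|
| All study eyes sphere-only | yes | no |
| One study eye, presbyopia-adjusted | no | yes |
| Two study eyes, both presbyopia-adjusted | no | yes |
| Two study eyes, one of each | no (fails *only*) | yes, with both eyes |

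Only the last kind causes a mismatch. No readable section defines a mixed category or assigns eyes by their own adjustment.

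**Step 2: does the readable text allow the last row?**
- Section 6 allows one or two eyes per subject, up to 200 eyes.
- Light treatment is given eye by eye: Section 7.3.2.5 has the operator select the eye to be treated.
- Section 7.2 puts the two surgeries on separate days.
- Ocular dominance is tested preoperatively and again at Postop Week 3, the visit of the first adjustment (Table 1).
- The presbyopia population in Section 5 is defined by bilateral implantation, not bilateral presbyopia adjustment.

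This permits mixed subjects but does not show that they occur. Text after the light-treatment sentence in the Synopsis and in Section 4 is blacked out and may settle the matter.

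**Step 3: would the fellow eye have data?** Footnote 2 to Table 1 triggers the tests by subject, so a sphere-only fellow eye would be tested and available to be counted.

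**Step 4: share of the table.** Take P presbyopia subjects, all bilateral, and let a share f of them have one sphere-only eye. Fellow eyes in the presbyopia tables = P × f. Total eyes there = 2P. Their share is m = P × f / 2P = f/2, so m runs from 0% to 50% whatever P is. Presbyopia subjects with a single study eye would lower the ceiling.

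**Step 5: effect on a percentage.** Let a be the rate in presbyopia-adjusted eyes and s the rate in sphere-only fellow eyes. The reported rate is (1 − m)a + ms, so the shift from a is m(s − a), at most half the difference between the two kinds of eye.

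Every input below except the 200-eye cap is an assumption: 100 bilateral subjects (200 eyes), P = 50.

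| f | 0% | 20% | 50% | 100% |
|---|---|---|---|---|
| Fellow sphere-only eyes (50 × f) | 0 | 10 | 25 | 50 |
| m = f/2 | 0% | 10% | 25% | 50% |
| Presbyopia-adjusted eyes (100 − 50f) | 100 | 90 | 75 | 50 |
| DCNVA 20/40 or better, a = 70%, s = 20% | 70% | 65% | 57.5% | 45% |
| UCDVA 20/20 or better, a = 60%, s = 90% | 60% | 63% | 67.5% | 75% |
| UCDVA, a = 70%, s = 80% | 70% | 71% | 72.5% | 75% |
| UCDVA, a = 90%, s = 60% | 90% | 87% | 82.5% | 75% |

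For example, at m = 25% the DCNVA row is 0.75 × 70 + 0.25 × 20 = 57.5. The last row swaps the rates of the first UCDVA row to show that the direction depends on the assumption.

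**The case against.** The strongest objection is that the harm rests on a kind of subject the readable protocol never says exists. The natural place for a rule on which eye gets which adjustment is just where the Synopsis and Section 4 are blacked out, and blacked-out text cannot be treated as missing. If both eyes of a presbyopia subject always receive the same type, m = 0 and nothing is wrong. This stands, and the point is therefore conditional. The rates and mixing fractions above have no source in the documents.

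The consequence is also limited. The study is exploratory, the presbyopia composite is binocular and per subject and so is unaffected, monocular DCIVA and DCNVA are not listed outcomes in Section 5, and additional analyses are already allowed. This stands too and lowers the priority. But an allowed analysis is not a planned one, and the stated rule would still produce the mixed table.

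Three stronger readings are tempting, and the documents do not support them.

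- *The Section 5 sphere-only percentage is wrong because it omits these fellow eyes.* In the illustration it would omit 10/110 = 9%, 25/125 = 20% or 50/150 = 33% of sphere-only eyes at f = 20%, 50% and 100%. But Section 7.2 leaves the refractive target to the physician, and Section 2 describes monovision, where the two eyes have different targets. A sphere-only eye in a presbyopia subject may not be aimed at best distance vision, so keeping it out is defensible.
- *The mixing hides a distance-acuity cost of the presbyopia adjustment.* This assumes that the fellow eyes see better at distance. With the target left open, the sign is unknown.
- *Footnote 2 to Table 1 is a second instance of the fault.* It sets who is tested, not how results are grouped. Testing both eyes is what makes a per-eye split possible.

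**Conclusion.** The point holds in conditional form. As written, Section 8.1.1 places a sphere-only fellow eye in the monocular presbyopia tables whenever its subject had a presbyopia adjustment in the other eye. The readable text permits such subjects, does not say whether or how often they occur, and may be qualified by the redacted paragraphs. The share of such eyes is between 0% and 50% of the monocular presbyopia tables if all presbyopia subjects are bilateral. The shift in any percentage is that share times the unknown difference between the two kinds of eye, in an unknown direction.

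This concerns the labelling and denominators of descriptive tables. No error rate is involved, and the binocular measures and the composite are correctly grouped. It is a change that could usefully be made, not one on which the study depends.

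**What to change.** In Section 8.1.1, state that for subjects who received a presbyopia adjustment, monocular UCDVA, UCIVA, UCNVA, DCIVA and DCNVA will be presented by the adjustment each eye received. Presbyopia-adjusted eyes (at least one presbyopia adjustment in that eye) and sphere-only fellow eyes then go in separate rows. Keep subject-level grouping for binocular measures and the composite. Leave the Section 5 sphere-only percentage restricted to sphere-only subjects, with the fellow eyes shown separately and not pooled into it.

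If the redacted text already rules out mixed subjects, one sentence in Section 8.1.1 saying so is enough, and the extra row would simply be empty.

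Cost: one or two sentences and one table row, with no new visit or test. Section 7.3.2.4 says adjustment procedures are recorded, but the case report form is not shown, so the sponsor should confirm that adjustment type is captured per eye. The drawback is a smaller denominator for presbyopia-adjusted eyes, by up to half if mixing is common (100 to 50 eyes in the illustration).
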